## II. Methods

i) Clinical evaluation and scoring. Before the patients are invited to participate, they have been thoroughly evaluated for correct diagnosis, including a complete clinical neurological examination, MRI of the head/brain (+/- spine/spinal cord), laboratory tests, etc. *The inclusion examination* ensures that inclusion criteria are fulfilled and that none of the exclusion criteria are met.

The study examinations include chinear examination and scoring as shown in the table.				
	Baseline	1. Random.per./3 mo.	2. Random.per./6 mo.	1 year
FTM-tremor scale*	Х	Х	Х	Х
Neurological exam.	Х			Х
QUEST	Х	Х	Х	Х
Adverse events reg.		Х	Х	Х
Neuropsych.exam.	X			Х
Video recording	Х	Х	Х	Х

The study examinations include clinical examination and scoring as shown in the table:

The Fahn-Tolosa-Marin tremor scale contains 21 items scored 0-4, with 0 indicating no tremor/disability and 4 severe tremor (constant, high amplitude)/inability to perform a task due to tremor. Item 1-9 score tremor for face, tongue, voice, head, trunk and the four extremeties. For face only rest tremor is scored, for tongue, head and trunk rest and postural tremor, and for the extremeties action/intention tremor is also scored. Items 10-13 test handwriting (for dominant hand only), and spiral drawing with right and left hand, and line drawing between defined points. Item 14 tests pouring of water from one plastic cup to the other. Item 15-21 describe functional disability of speaking, feeding (not liquids), bringing liquids to mouth, hygiene, dressing, writing, working.
A video recording of the objectively tested items of the FTM was not originally planned from the ouset, but we realized it was useful and has been performed from patient # primarily to document

the phenomenology of tremor at baseline and of resttremor at follow-up. All patients have given their oral consent to these video recordings. Written consent will be collected before these video recordings are actively used to support data analysis.

- *Quantification of tremor using an electronic device carried on the patient's wrist, such as the* ActiwatchTM (actigraph) was originally planned to be part of the tremor evaluation. But these device-based measurements was not performed in this study, as they became too expensive.

- Quality of life in Essential Tremor- scale (QUEST). A 30 item questionnaire developed specifically for tremor patients, evaluating quality of life, cognitive, and emotional aspects of the tremor (20).

-VAS of Global Disease Burden (patient evaluated) and of tremor related pain. Visual analogue 0-10 centimeter continuous scale, on which the patient scores at which severity they assess the global tremor disease burden and tremor related pain.

**ii) Operation.** Preoperative axial MRI sequences (T2-weighted fast-spin-echo, diffusion-weighted spin-echo echo-planar imaging, and 3D inversion prepared T1-weighted gradient-echo) will be obtained on a 3 Tesla MRI-scanner the day before the operation. In local anaesthesia a CRWTM stereotactic frame, (Radionics, MA, USA) is mounted, placed parallell to the AC-PC line, before performing a stereotactic 3D CT scan. The MRI and CT scans are merged using the iPlanTM (version 3.0) computer-aided neuronavigation system (BrainLAB, München, Germany), or updated versions, which is also used to plan the targets based on predefined stereotactic coordinates for VIM and PSA, refined according to relationship to the MRI-visible STN and RN. Trajectory angle will be chosen to cover VIM and to enter PSA slightly posterior and medial to STN, at the level of maximal diameter of RN. To ensure safety, trajectories are always planned to avoid vessels, sulci and ventricles. If the trajectory angle needed to reach both targets is judged to compromise safety, the trajectory is adjusted so that the PSA is still reached, and as close to the preferred VIM-target as possible.

Microelectrode recordings (MER) were not performed. This was decided prior to inclusion of the first patient.

Clinical test stimulation is performed in the awake patient on the implanted permanent quadripolar electrode (model 3389 or 3387, Medtronic, MN, USA, or Boston Scientific Cartesia electrode), at 4 levels, corresponding to the four levels of the electrode contacts (for both the Medtronic and the Boston electrode, each electrode level spans 1,5 mm, with 0,5 mm spacing between electrodes). This should confirm good tremor suppression and no unaccepatable side effects, otherwise a second trajectory is chosen, based on anatomical considerations to improve effect on tremor, or avoid the unacceptable side-effects.

Electrode position is checked using perioperative radiography, and the electrodes fixed to the scull. After removal of the stereotactic frame, the electrodes are connected to a dual pulsegenerator (Activa PC or RC, Medtronic, or Gevia, Boston Scientific) implanted in the subclavicular region.

**iii) Randomization periods/stimulation treatment.** Half the patients are randomized to receive VIM-stimulation from 0-3 months after surgery and then switched to receive PSA-stimulation for the next 3 months, and the other half to receive PSA-stimulation the first three months and VIM-stimulation the next 3. During these two randomization periods the pulse width will be 60 microsec and frequency 130-145 Hz, monopolar and ring-stimulation mode (bipolar mode only if monopolar leads to intolerable side effects). Current should not exceed 3 mA during the randomization periods. After scoring at the end of the last 3-month randomization period, the electrode contact yielding the best tremor reduction with no or only minor/possible side effects is chosen for further treatment. During follow-up to 1-yr post-op there may be 2 additional visits for optimal adjustment of stimulation parameters. This protocol may be deviated from only if the above limitations clearly provide the patient with unsatisfactory treatment results.

Randomization: Stratified block randomization, performed by a secured web-based service (provided by The Norwegian University of Science and Technology, Trondheim, Norway (http://webcrf3.medisin.ntnu.no). The project leader enters each new patient for randomization after inclusion and operation/implantation of the DBS-system.

iv) Neuropsychological examinations. A standard set of well-known and validated neuropsychological tests will be performed pre-op and 1-yr post-op.

v)  Fluoro-deoxy-glucose-PET (FDG-PET). This could not be performed due to too high costs.

**vi) Imaging analysis to show anatomical position of implanted electrodes/active contacts.** The pre-op MRI and a post-op helical CT-scan are exported via CD's to the soft-ware SureTune (Medtronic), to show the localization of the implanted electrodes (and the active contacts used) on the patient's brain anatomy, as visualized by MRI. This work is done using the Visual Lab portifolio developed by the University Clinic Wuerzburg by [name] and [name] (see 2.3.), and is supervised by them.

vii) **Long-term, open follow-up extension.** All participating patients who complete the first year of the study will be invited to participate in an open, long-term follow-up study. Study examinations will be performed at 2 years and 3, 5, 7,5 and 10 years after the operation. The FTM-tremor score, neurological examination, the QUEST quality of life-questionnaire and the HAD-questionnaire will be performed. The TETRAS score will be performed in a subset of patients in whom this score was also obtained at baseline.

viii) **Power calculation and plan for statistical analyses,** Based on earlier research on deep brain stimulation in VIM and PSA for tremor, we assume a mean change (improvement) from baseline to the end of the two randomized 3 months treatment periods of 16 points (standard deviation SD=5) in our primary endpoint (composite FTM-tremorscore of contralateral arm). (Power calculation is done for dominant arm). We defined a clinically significant difference as 1.8 points between the two interventions. Furthermore, we assume a SD of differences of 4. When the sample size in each period is 41 and the number of subjects for each intervention is equal, this 2x2 cross-over design will have 80% power to detect a difference in mean change between interventions of 1.8 points using a paired t-test. In order to account for potential drop-out and missing data, 45 patients will be randomized.

Continuous and categorical data will be described with mean (SD) and number of observations (percentage), respectively. A basic statistical analysis of the 2x2 cross over design assumes no period (systematic difference between periods) and carry over (systematic difference between orders of received interventions) effect. We will assess period effect by comparing the mean response of the two periods using a paired t-test and carry over effect by comparing the mean response of the two orders of received interventions using an independent t-test. If the tests for period and carry over effects are non-significant, these effects are considered absent. Thus, a paired t-test of treatment difference gives an estimate of the treatment effect with 95% confidence interval and p-value.

In addition, we will conduct a linear mixed model approach using a random intercept with maximum likelihood estimation to account for within-subject correlations and fixed effects for treatment, period, and carry-over (interaction between period and treatment). If the period and carry over effect are non-significant, we will re-estimate the mixed model omitting these terms. If the period or carry over effect is significant, we will re-estimate the mixed model analysis including respective significant terms and report treatment effect with 95% confidence interval and p-value adjusted for period or carry over effect. With no missing data or drop-outs, the t-test and mixed

model approach should give equal results. In case of missing data, drop-outs or discrepancy between the t-test and mixed model approach, the mixed model approach will be our conclusive analysis. A p-value < 0.05 is statistically significant.

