## 2.2. Approaches, hypotheses and choice of method

To overcome the limitations of today's standard method of treating severe action tremors with VIM-DBS, we will now collaborate with one of the world's leading DBS experts ([name], Germany), to perform the first double-blind, randomized, controlled and comparative study of VIM-DBS versus PSA-DBS in patients with disabling action tremor. This will entail an interdisciplinary approach that combines cutting edge neurosurgical intervention, neurophysiological manipulation, brain imaging, and neurological and neuropsychiatric assessment. In combination, these methods will provide novel insight into the design of DBS for action tremor, and help provide a platform in Norway and internationally for making similar advances in the use of DBS as a therapeutic tool for other neurological disorders.

We will implant one quadripolar (or octapolar) electrode so that it covers both targets on one side, unilaterally or bilaterally as indicated clinically. The efficacy of stimulating each target will be studied in individual patients and between patient groups in a cross-over design, in two consecutive 3-month periods, by the use of validated tremor scores. Further continuous stimulation of the most effective target in each patient will be evaluated after another 6 months. This will provide unbiased efficacy-data about the two targets, both within each patient, and between patient groups. Stimulation efficacy will also be evaluated in relation to the exact target localization, defined by merging post-op helical CT scan (shows the four electrode contacts), with pre-op MRI (the MRI protocol includes DTI uptake for fiber tracking.) Such high-resolution correlation data has to date only been published in a few action tremor patients world-wide, and will add extremely important new data to aid DBS targeting in the future. Since little is known about whether cognitive functions are altered by the disease or the treatment, we will perform neuropsychological testing before and after effective DBS treatment.

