## I. Study overview.

- Study design: Single-center, prospective, randomized, double-blind. Cross-over.

- Number of patients to be included: Minimum 44.

- Inclusion criteria: Patients of both genders aged 18 – 80 years. Min 5-yr duration chronic action tremor of upper limb(s), w/ or w/out tremor of head/neck, trunk, lower limbs, who have insufficient relief from adequate trials of recommended medications. The arm tremor must be so severe that it interferes with the patient's work performance or activities of daily living, such as drinking/eating, dressing/hygiene, and/or writing. Clinical diagnosis (according to criteria defined by the Consensus Statement of the Movement Disorders Society (5)) include ET, DT, CbT- idiopathic or secondary (to e.g.MS or SCA), or severe PD tremor (who are not eligible for DBS of the subthalamic nucleus). A new clinical classification of tremor syndromes published in 2018 will also be used to support/update the clinical classification of the study population (18).

- Exclusion criteria: Brain MRI showing so marked general atrophy, or supra-tentorial white matter changes, that the safety of the procedure is affected. Co-morbidity of dementia or other severe neuropsychiatric disorder (major depression or anxiety disorder, active/recent psychosis, drug or other substance abuse). Increased risk of bleeding, cancer at advanced/not stabilized stage, other co-morbidity with short life expectancy. Other surgical contraindications.

- Identification of the surgical target: The quadripolar electrode will be placed so that each target (VIM and PSA) is covered by at least one of four electrode contacts. The targets will be found using

preoperative MRI (3 Tesla) merged with helical/3D CT, according to predefined coordinates, refined by relation to neighboring MRI-visible structures (STN and RN). Electrode trajectories will be defined to avoid cerebral sulci, vessels and ventricles.

- Primary endpoints: 1) The difference in the change from baseline to the end of each of the two 3month cross-over periods in *the objectively observed tremor of the contralateral upper limb(s)*, as evaluated by items 5 (right)/6 (left),10 (for dominant hand only), and 11-14, in the Fahn-Tolosa-Marin (FTM)-score (19), with VIM- versus PSA-stimulation. *Functional disability of arm tremor* (items 16-21) is also part of the primary endpoint evaluation.

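### The protocol says each electrode covers both targets but allows VIM alone to be approximated, and its primary comparison has no link to the planned imaging that would show the effect of a missed VIM

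*Protocol*

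**What the plan says.** The opening of protocol section 2.2 says one electrode is implanted "so that it covers both targets on one side, unilaterally or bilaterally as indicated clinically". Section 2.2 I (Study overview) says the same: "The quadripolar electrode will be placed so that each target (VIM and PSA) is covered by at least one of four electrode contacts". Neither place mentions an exception.

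Section 2.2 II ii (Operation) starts from the same intention but adds a fallback. The trigger is "If the trajectory angle needed to reach both targets is judged to compromise safety", and the action is that "the trajectory is adjusted so that the PSA is still reached, and as close to the preferred VIM-target as possible". No distance limit is given. Nor does the text say which contact then counts as VIM, or how such patients enter the comparison. If awake test stimulation is unsatisfactory, "otherwise a second trajectory is chosen, based on anatomical considerations to improve effect on tremor, or avoid the unacceptable side-effects"; coverage of both targets is not restated there.

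Section 2.2 II iii fixes the order of events: "The project leader enters each new patient for randomization after inclusion and operation/implantation of the DBS-system".

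On imaging, section 2.2 says "Stimulation efficacy will also be evaluated in relation to the exact target localization", and section 1 says much the same. Sections 2.2 I, 2.2 II vi and 2.3 describe localising the active contacts from pre-operative MRI and post-operative CT, including those used at 3 and 6 months. The analysis in section 2.2 II viii is a paired t-test plus a mixed model with treatment, period and carry-over. Contact location does not appear in it.

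Of the cross-over, section 2.2 claims: "This will provide unbiased efficacy-data about the two targets, both within each patient, and between patient groups".

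**The concern.** The trial asks which target suppresses tremor better. That requires each patient's VIM period to be stimulation of VIM and each PSA period to be stimulation of PSA. The fallback treats the targets unequally: PSA is kept and only VIM gives way. A patient in whom VIM is missed would contribute an on-target PSA period and an off-target VIM period.

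The cross-over does not protect against this. Lead position is settled at surgery, before the sequence is allocated, and stays the same through both periods. Both sequences therefore carry the same one-sided displacement. Blinded scoring does not touch it, and the period and carry-over tests look for something else. A PSA advantage could then partly reflect VIM contacts off target rather than a better target. The protocol's own background (section 2.1, Stimulation of VIM) lists suboptimal electrode placement among the debated reasons for loss of VIM benefit.

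**Working it through.** **Reproducing the protocol's figure.** Inputs from section 2.2 II viii: difference 1.8 points, SD of within-patient differences 4, power 80%, significance level 0.05 (taken as two-sided, which is an assumption), paired t-test. With the noncentral t distribution, noncentrality (1.8/4)·√n and n − 1 degrees of freedom, power is 0.793 at n = 40 and 0.803 at n = 41. The stated 41 is confirmed, so the sample size is not in dispute.

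**Form of the shift.** Let D be improvement under PSA minus improvement under VIM in the same patient. Let f be the share of patients with VIM not covered and L the mean points of VIM improvement lost in them. Then

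mean observed D = true difference + f·L.

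Sequence does not enter the formula, so balancing the order leaves f·L unchanged.

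**Size.** The protocol gives neither f nor L; the values below are assumptions. To find the chance of a significant result when the targets are truly equal, I took n = 41, variance 16 + f(1 − f)L² and the same t-test.

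| f | L (points) | Shift f·L | Share of 1.8 | SD of D | P(significant) if no true difference |
|---|---|---|---|---|---|
| 10% | 2 | 0.2 | 11% | √16.36 = 4.04 | 6% |
| 20% | 4 | 0.8 | 44% | √18.56 = 4.31 | 21% |
| 30% | 6 | 1.8 | 100% | √23.56 = 4.85 | 64% |

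For scale, 6 points is 6/16 = 38% of the 16-point improvement assumed in the power calculation, so the last row is an upper case. In the first row the shift is minor.

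**Precision of a restricted analysis.** The same power formula was applied to patients with both targets covered:

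- 20% excluded from 45 randomised: 36 patients, power 0.75.
- 20% excluded from 41 evaluable: 32.8, about 33 patients, power 0.71.
- 30% excluded from 41 evaluable: 28.7, about 29 patients, power 0.65.

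**Validity of that subset.** Whether some contact on the lead covers each target is fixed at implantation, and randomisation comes afterwards. Selecting on lead coverage is therefore selection on a pre-randomisation characteristic, and the comparison within the subset stays randomised.

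**The case against.** A reader might infer that the protocol has no means of detecting a missed VIM. The text does not support this. Contacts are to be localised, including those in use at the two cross-over endpoints, and efficacy is to be related to location. An off-target VIM contact could be seen there. What is absent is a link from that work to the primary comparison.

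A reader might also infer that the comparison is biased as a matter of fact. That is not supported either. The protocol does not say how often the fallback was expected or used. Moving away from a preferred coordinate does not by itself mean that no contact covers the nucleus. Awake test stimulation at all four contact levels is a relevant check, although it tests tremor suppression and side effects rather than coverage of VIM.

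The conflict can be read as a general rule followed by a safety exception, in which case a cross-reference would mend the wording. That is fair as to the text. It does not remove the one-sidedness of the exception or the need to know how often it applied.

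A definition of coverage and a sensitivity set are often left to a SAP, and one not shown here may contain them. For that reason their absence from the protocol is not itself the criticism. A SAP would not reconcile the coverage statements or make the unqualified claim of unbiased data correct.

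Finally, the protocol says VIM cannot be seen on MRI and that its coordinates vary between centres, so classifying coverage needs a reference. The predefined coordinates used for surgical planning can serve.

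**Conclusion.** The point holds in a limited form. The coverage statements in section 2.2 and its Study overview disagree with the fallback under Operation and must be reconciled. The fallback is one-sided. Where it leaves VIM uncovered and lowers the VIM effect, the primary difference moves towards PSA, and randomised order, blinding and the planned period and carry-over tests do not correct this.

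The direction is known under those two conditions; the size is not. The assumed values give 0.2 to 1.8 points against a 1.8-point target difference, from minor to decisive, and nothing in the protocol says where in that range the trial lies. This is a worthwhile and inexpensive improvement to the analysis. It does not show that the result is wrong, and it takes no position on which trajectory is clinically right.

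**What to change.** 1. Reconcile the opening of section 2.2, the Study overview and the Operation text, leaving the surgical rule to the clinicians.
2. Before outcome data are joined, and blind to them, have the imaging laboratory classify each lead from the existing MRI and CT: is VIM covered by a contact, and is PSA, judged against the predefined coordinates? Classify coverage by the lead, not the contact switched on, so that the classification rests on something fixed before randomisation.
3. Report the number of adjusted trajectories and the number of patients with VIM not covered.
4. Repeat the primary model as a prespecified sensitivity analysis in patients with both targets covered. Report the estimate and confidence interval beside the full-sample result.
5. Attribute a difference to the target itself in the light of both estimates, without a formal gating rule. Requiring agreement in size would need a margin that the documents do not supply, and would make the conclusion depend on an underpowered subset.
6. Qualify the claim of unbiased data in section 2.2 accordingly.

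The cost is a short classification exercise and one further model run on imaging already planned. The drawback is the lower precision of the restricted estimate shown in the working. Its result also applies only to patients whose lead covers both targets.

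### The primary analysis is chosen by pretests for period and carry-over, and the carry-over-adjusted treatment effect is undefined: depending on unstated coding, it inflates the type I error to about 8% or adjusts for nothing

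*Protocol*

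**What the plan says.** The statistical part of the protocol (section 2.2, II. Methods, viii) sets out two routes to the VIM-versus-PSA comparison.

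- **t-tests.** Period is tested with a paired t-test, and carry-over with an independent t-test between the two orders. Then: "If the tests for period and carry over effects are non-significant, these effects are considered absent", and a paired t-test gives the treatment effect.
- **Mixed model.** It has a random intercept and "fixed effects for treatment, period, and carry-over (interaction between period and treatment". Non-significant period and carry-over terms are removed and the model is refitted. Significant ones stay, and the plan is to "report treatment effect with 95% confidence interval and p-value adjusted for period or carry over effect".

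The mixed model decides if data are missing, patients drop out or the two routes disagree. The only error rate stated is "A p-value < 0.05 is statistically significant". Nothing allows for the data-driven choice of model, and nothing says which contrast is the treatment effect once the interaction is in the model.

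**The concern.** This is the two-stage cross-over procedure, and it raises two problems on the trial's main comparison.

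First, the carry-over test is a between-patient test in two groups of 22 and 23. It is weak, so a non-significant result says little about whether carry-over is absent.

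Second, the adjusted effect reported after a significant carry-over test is not what its name suggests. It may be a between-patient comparison, correlated with the very test that selected it, or the ordinary within-patient comparison under another label. A chance finding could therefore change the estimand, the precision and the error rate of the reported result, and two analysts following the text could report different answers from the same data.

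**Working it through.** **Inputs (Methods, viii).** "We defined a clinically significant difference as 1.8 points between the two interventions". "Furthermore, we assume a SD of differences of 4". Change from baseline: "16 points (standard deviation SD=5) in our primary endpoint". Evaluable patients 41, randomised 45, equal split between orders (22/23 used here). Assumptions: two-sided 5% level, normal data, and SD 5 in each period.

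**1. The plan's own figure.** The plan states that "this 2x2 cross-over design will have 80% power to detect a difference in mean change between interventions of 1.8 points using a paired t-test". The SE is 4/√41 = 0.625. The exact noncentral-t power is 80.3% at n = 41 and 79.3% at n = 40. The figure is reproduced.

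**2. Implied correlation.** SD of differences² = 2·SD²·(1 − ρ), so ρ = 1 − 16/(2·25) = 0.68.

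**3. Why the interaction is the order term.** Call the orders A (VIM then PSA) and B (PSA then VIM), with cell means A1, A2, B1, B2. The period-by-treatment interaction is

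(A1 − B1) − (B2 − A2) = (A1 + A2) − (B1 + B2),

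which is the difference between orders. Four cell means give three contrasts: treatment, period and order. None is left to separate carry-over from order.

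**4. What the treatment coefficient becomes with the interaction kept.** Random-intercept models fitted to simulated data confirm both cases:

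- Reference coding: A1 − B1, the period-1 between-patient difference. SE = 5·√(1/22 + 1/23) = 1.49.
- Centred (sum) coding: ½[(A1 − A2) − (B1 − B2)], the within-patient contrast, up to the scale of the coding. SE = (4/2)·√(1/22 + 1/23) = 0.60.

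**5. Power of the carry-over test.** SD of a patient's mean = 5·√((1 + 0.68)/2) = 4.58. SE between orders = 4.58·√(1/22 + 1/23) = 1.37. A differential carry-over λ shifts the difference between orders by λ/2 and biases the within-patient treatment effect by the same λ/2.

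| λ (points) | Bias (points) | Power of the test (43 df) |
|---|---|---|
| 1.8 | 0.9 | 9.9% |
| 3.6 | 1.8 | 25.1% |

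The second row is a bias as large as the target difference, missed three times in four.

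**6. Type I error of the whole rule.** The period-1 contrast and the carry-over contrast have correlation √((1 + 0.68)/2) = 0.92. By simulation (200,000 trials per setting, no treatment, period or carry-over effect), the carry-over test is falsely significant in 5% of trials, and the period-1 contrast then rejects in about 62% of those. Hence roughly 0.05 × 0.62 + 0.95 × 0.05 = 0.0785.

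| Reading of the rule | Type I error |
|---|---|
| Reference coding, ρ = 0.68, N = 41 to 45 | 7.8–8.1% |
| Only the significant terms literally kept | 7.2% |
| Reference coding, assumed ρ from 0.2 to 0.9 | 6.8–8.9% |
| Centred coding | 5.0–5.1% |
| Period pretest only, no carry-over branch | 5.0–5.1% |
| Treatment and period always fitted | 4.9–5.0% |

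**7. Power for 1.8 points.** The period-1 contrast alone has about 22%. The within-patient analysis with period fitted has about 84% at 22/23.

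**8. Does the pretest protect when carry-over is real?** With no treatment effect and a carry-over of 2 points, the carry-over test is significant in about 11% of trials. The whole rule still rejects in about 35% under reference coding and 36.5% under centred coding. The paired t-test alone rejects in about 34%.

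**The case against.** The strongest reply is that the harm is narrow. Error inflation needs a significant carry-over test, about one null trial in 20. In the rest, the result is the within-patient analysis with or without period. With a true 1.8-point effect the whole rule keeps about 82–83% power at 22/23, even under reference coding. Nothing in the protocol shows that carry-over of 1.8 or 3.6 points is expected. All of this stands. It limits the size of the problem but does not make the rule sound.

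Three stronger readings are tempting, and the protocol does not support them.

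- **That the type I error simply is 8%.** The protocol fixes neither the coding nor the contrast. Under centred coding there is no inflation. The ambiguity is itself the defect.
- **That no carry-over-free effect can be estimated.** The period-1 difference can be estimated and is untouched by carry-over. It is imprecise and correlated with the pretest. What cannot be had is a *within-patient* effect free of carry-over.
- **That the period pretest inflates the error rate or costs much power.** It adds no material inflation. The plan keeps a significant period term, so even with a true 2-point period effect, power before the carry-over branch stays near 84%. The background section describes loss of tremor control with VIM over months and years, which does not establish a shift between month 3 and month 6.

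**Conclusion.** The rule is wrong as written. It infers absence from a test with about 10% power for a 1.8-point carry-over and 25% for 3.6 points. It also promises a carry-over-adjusted treatment effect that is either a low-powered between-patient contrast selected by a correlated pretest (type I error about 8%) or an effect not adjusted for carry-over at all (type I error 5%). The excess comes from the carry-over pretest alone.

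The sizes rest on the protocol's SDs of 5 and 4 (ρ = 0.68), a 22/23 split, normal data and a two-sided test. Across assumed correlations of 0.2 to 0.9, the error under reference coding runs from 6.8% to 8.9%. That the interaction and order are the same term rests on no numerical assumption.

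**What to change.** Replace the pretest rules with one fixed primary analysis: a linear mixed model with treatment and period always included, a random intercept for patient and no carry-over term. Delete the statement that non-significant effects are absent, the refitting steps and the carry-over-adjusted estimate. Show results by order and period descriptively. Argue from the design that carry-over is negligible (3-month periods, scoring at the end of each), and say plainly that the analysis holds the 5% error rate but leaves any carry-over bias in place.

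The cost is wording and one degree of freedom: power at n = 41 goes from 80.3% to 80.2%. No new data or patients are needed.
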